**Modification Request Information**

Select One:

This modification does not increase risk to study participants.  
 This modification may or will increase risk to study participants.

Is this modification request due to an Unanticipated Problem/Adverse Event, or Protocol Violation?

Yes  No

In your professional opinion, does this modification involve information that might relate to a subject's willingness to continue to take part in the research?

Yes  No

If yes, state how the information will be communicated to subjects (i.e., re-consent, send letter, etc.):

**For each proposed modification, include a justification.**

Example: [name], is being added as co-investigator because she has expertise with the subjects on this protocol. She has completed human subject protections training, and is authorized to obtain consent.

**\*\*\* If this modification changes the scope of your activities to include COVID-19 related research, please insert "COVID19" at the start of your Project and Short Titles.\*\*\***

Addition of the Situational Assessment of Activity and Function (SAAF) assessment.

The SAAF is a new assessment created by current study PI ([name]) to gain better insights on the situational characteristics that cause behavioral reactions in persons with dementia. The SAAF was developed from initial data collection of the current study. The SAAF is 120 questions to be completed by caregivers of persons with cognitive impairment and will take approximately 15 minutes to complete.

Questions review caregiver perceptions of the activity performance of the person they care for in various activities (i.e., cooking, dressing, community mobility, etc.) The assessment is completed electronically using Redcap survey emailed to caregivers. Use of the SAAF in this study is to glean initial reactions from caregiver participants regarding their ease of use and to determine time length of administration. The use of the SAAF in this study will be completed using REDCap public survey link. This feature allows individuals to complete the survey, but does not associate a record ID to answers, all responses are anonymous. Data from survey item responses will not be stored, saved, reviewed or analyzed. Caregivers currently enrolled in this study will be asked to voluntarily complete the electronic survey if they would like. It is not required. Participants will be asked to disclose the length of time

61291  
CLOSED

it took to complete the form and to document any initial perceptions of the ease of use of the form and/or it's perceived applicability.

Your protocol has been submitted.

## Statistical Analysis

Participants' characteristics were compared among the three arms using analysis of variance (ANOVA) for continuous measures and chi-square tests or Fisher's exact for categorical measures. The analysis of the primary endpoint used a chi-square test to compare the proportion of participants completing at least 75% of the video sessions among the study arms. The analysis of all secondary and exploratory endpoints relied on a modified intention-to-treat (mITT) strategy in which participants were included in the analysis only if the dyad completed at least one video session. For those endpoints, the main analysis tool was ANCOVA in which the mean value of an endpoint at the end of the intervention period was adjusted for baseline and then compared among the study arms. Sensitivity analyses were conducted in which multiple imputation was used for missing responses at the end of the intervention period (regressed on baseline) and in which the list of covariates included age of the person with AD at baseline and gender of the caregiver when appropriate. These sensitivity analyses did not change any of the conclusions drawn from the reported ANCOVA in Table 3 and are not reported here. A further sensitivity analysis included the measurements made at the four-week follow-up and relied on ANCOVA to compare the profile of responses at the end of the intervention and at the four-week follow-up each adjusted for baseline. This analysis did not change the conclusions drawn from Table 3 and is not reported here. All analyses were done using PC-SAS, Version 9.4.

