For this study, the following step-by-step sequence will be used. Recruitment will occur via discussion with SBCOA medical team (MD/APRN/PA) and [name] of appropriate referrals of heightened cognitive impairment with behavioral disturbance. Additionally, SBCOA records will be reviewed for all eligible cohort participants. These participants will be contacted via SBCOA recruitment team with calling, mailing, and/or emailing eligible participants with an invitation to participate in the current study. Following agreement to participate, SBCoA staff and researcher will coordinate with the participant a date and time for Visit 1 to be completed via a virtual telemedicine platform. All visits within this study will be scheduled at times convenient for the participants using telemedicine Zoom video conferencing. Videos will be recorded and saved on private and secure server hosted by Sanders-Brown Center on Aging Data Management Team.

During the screening visit, a research assistant or PI will review and obtain consent as described above, talk with the LAR and caregiver to determine eligibility status, and record medications. The PI will complete a UKADC or KNI chart review of medical conditions, medications, and symptoms from the prior 24 months if available. Records will be assessed for most recent vital signs (systolic and diastolic blood pressure, pulse, temperature, and respiration), known allergens, chronic medical conditions, recent medical changes, and medications. The PI (OT) or UKADC medical staff (MD/APRN/PA) will conduct a physical and neurological examine via Telemedicine. The physical examination will include skin, head/ears/eyes/nose/throat (HEENT), oral/teeth/gums (history of dental problems/dentures), sensory function, gait/walking ability, and musculoskeletal range of motion of upper extremities. All complete physical and neurological examination data will be entered on the appropriate CRF. Neurological assessment will include of cranial nerves, strength, coordination, symmetry of movements, and movement speed. Verbal assessment of patients' sensory function (including hypersensitivity) with caregiver will occur at the screening. Significant abnormalities consistent with disease processes will be documented.

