Once eligibility is confirmed, the research assistant will email a REDCap link to the caregiver for the Zarit Caregiver Burden and the Adult Sensory Profile, Actigraph and charger, and a copy of consent forms to the participant's caregiver. The PI will complete the COPM on visit 1, and provide caregiver and participant with Actigraph wear and care instructions. The VABS will be emailed to the caregiver via a confidential link through Pearson Publishing.

Subjects will be randomized to treatment arms by the statistical team. Participants will be randomized into one of the three groups: control, standard environmental design protocol, individualized environmental design protocol. Recruitment will be ongoing until all groups have 10 participants. In the event of drop out or early termination (causes will be recorded), researchers will recruit for replacement participants so that the study is completed with 30 entire study duration cases.

Visit 2 will consist of baseline assessment. A research assistant or the PI will complete the MOCA, with the participant with dementia. The caregiver will complete the NPI. Following Visit 2, an occupational therapist will be provided results of the COPM and ASP for participants of the individualized treatment arm. A sensory protocol will be developed based on assessment results following predetermined guidelines. All intervention materials for all study participants will be mailed to caregivers within 4 days of Visit 2. Upon receipt of intervention supplies, caregivers will contact the PI or occupational therapist for study initiation. Visit 3 will provide caregiver training for intervention use and initiation of Actigraph use. Adverse events since Visit 2 will be recorded. Visit 3 marks day 1 of intervention implementation. Participants will mail Actigraph back to UKADC in provided pre-paid envelop following week one of intervention.

Visits 4-8 will be scheduled at the end of each week following Visit 3. The PI, occupational therapist, or research assistant will record concurrent medication, and adverse events. With the caregiver, the interviewer will review behaviors observed by the caregiver, the behavior journal, compliance and acceptance of the intervention by the caregiver and the person with dementia. Actigraphs will be mailed from UKADC to participants, and patient will be asked to wear actigraph for last week of intervention window.

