Visit 9 will conclude the intervention window at the end of week 4. The PI, occupational therapist, research assistant will record adverse events, concurrent medication, Actigraph, and weekly behavior journals/compliance. The research assistant will conduct the NPI, COPM, VABS with the caregiver and the MOCA with the person with dementia. A member of the SBCoA medical team will conduct a physical and neurological exam. Due to the length of assessments within Visit 7, this session may be split and completed in more than one Zoom conference. The Zarit Caregiver Burden Scale will be emailed or mailed to the caregiver with prepaid envelop for return.

A four-week follow up will be conducted at Visit 10 whereby the research assistant will conduct the NPI, COPM, VABS with the caregiver, and the MOCA with the person with dementia. A member of the SBCoA medical team will conduct a physical and neurological exam. The Zarit Caregiver Burden Scale will be emailed or mailed to the caregiver with prepaid envelop for return.

Schedule of events can be found in attached detailed protocol.

A list of potential items sent in sensory kit is attached here.

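### If the mITT rule's video session means an intervention session, the secondary and exploratory comparisons drop randomised dyads on a post-randomisation condition; the term is undefined and the number dropped is not given

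*Combined protocol and SAP*

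**What the plan says.** The Statistical Analysis section sets the rule and its scope. "The analysis of all secondary and exploratory endpoints relied on a modified intention-to-treat (mITT) strategy", under which "participants were included in the analysis only if the dyad completed at least one video session". On that set, "the main analysis tool was ANCOVA in which the mean value of an endpoint at the end of the intervention period was adjusted for baseline"; the three arms are compared on these adjusted means. The primary endpoint, the proportion of participants completing at least 75% of the video sessions, is not placed under this rule.

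The sensitivity analyses cover multiple imputation of missing end-of-intervention responses from baseline, added covariates, and the four-week follow-up. None is said to restore dyads that the rule removed. No all-randomised analysis of these endpoints is described.

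The timing has to be read from Research Procedures:

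- On visit mode: "All visits within this study will be scheduled at times convenient for the participants using telemedicine Zoom video conferencing". Screening, Visit 1 and Visit 2 are therefore on video too.
- On allocation: "Subjects will be randomized to treatment arms by the statistical team". This stands after eligibility and Visit 1 and before Visit 2; no exact day is given.
- On supplies: "All intervention materials for all study participants will be mailed to caregivers within 4 days of Visit 2". Caregivers make contact once the supplies arrive, and Visit 3 is day 1 of the intervention.
- On caregiver burden at week 4: "The Zarit Caregiver Burden Scale will be emailed or mailed to the caregiver with prepaid envelop for return". The NPI, COPM, VABS and MoCA are collected at Visit 9.

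Under Study Design, caregivers deliver the intervention. During the study the control arm receives a pamphlet, with a sensory kit offered only after follow-up.

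**The concern.** An intention-to-treat label tells readers that the arms are compared as randomised. A rule that depends on what a dyad does after allocation breaks that assurance if the dyads removed differ in prognosis and are removed unequally across arms. Here the caregiver cannot be masked to what is delivered. A caregiver who receives only a pamphlet, or a kit that does not appeal, can decline to start and drop out of the behaviour, cognition and burden comparisons.

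Dyads with no session are also the clearest failures on the primary feasibility endpoint. The secondary estimate would then describe dyads willing to start, not dyads randomised. Baseline adjustment removes only the part of the difference that the baseline score explains. The plan defines neither the session nor the numbers removed, so a reader cannot tell whether any of this happened.

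**Working it through.** The documents give no power calculation or bias figure to reproduce. The planned size is 3 x 10 = 30, chosen for feasibility.

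**1. What the rule can mean**

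| Reading of video session | Timing | Effect |
|---|---|---|
| Any Zoom visit, including screening | Before randomisation | Every randomised dyad qualifies; nobody is removed |
| Any Zoom visit after randomisation, including Visit 2 | After randomisation, but can be met before the mailing | Can remove dyads; arm materials not yet seen |
| Intervention sessions, Visit 3 onward | After randomisation and after the mailing | Can remove dyads who have seen their arm's materials |

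The third reading fits best, because the primary endpoint counts completed video sessions as a measure of taking part. It remains an inference.

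**2. Size by identity**

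Let f be the share of an arm removed, and D the removed-minus-retained difference in SD units. The all-randomised mean is (1 - f) x retained + f x (retained + D) = retained + f x D, so removal shifts the arm mean by f x D. With 10 per arm, each dyad is 10% of its arm. For assumed f of 10-20% and D of 0.5-1 SD:

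- 0.1 x 0.5 = 0.05 SD
- 0.1 x 1 = 0.10 SD
- 0.2 x 0.5 = 0.10 SD
- 0.2 x 1 = 0.20 SD

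**3. Size by simulation of the planned ANCOVA**

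Assumptions: 10 per arm, baseline-outcome correlation 0.6, no true effect. A share of dyads is worse at week 4 than baseline predicts. Those dyads leave before the first session in both active arms and never in control. The contrast is the average active arm against control; negative values favour the active arms.

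| Share, shortfall | Bias with removal (6,000 runs) |
|---|---|
| 10%, 0.5 SD | -0.052 |
| 10%, 1 SD | -0.107 |
| 20%, 0.5 SD | -0.096 |
| 20%, 1 SD | -0.197 |

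The standard error is near 0.34, so the bias is about 0.05/0.34 = 0.15 to 0.20/0.34 = 0.59 of a standard error. If the loss is in control instead, the sign reverses.

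A second mechanism removes 1, 2 or 3 of 10 dyads from one arm, with the propensity to leave correlated 0.5 with outcome (20,000 runs). The bias is 0.054, 0.103 and 0.148 SD, and the type I error of a nominal 0.05 test is 0.052, 0.058 and 0.061. Removing the same numbers at random gives bias of about 0 and type I error of about 0.05.

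**4. Does imputation repair it?**

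The scenarios of step 3 were run again (3,000 runs each), treating the week-4 outcomes of the lost dyads as missing and imputing them:

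| Share, shortfall | Removed | Imputed from baseline | Imputed from baseline and arm |
|---|---|---|---|
| 10%, 0.5 SD | -0.049 | -0.047 (96% kept) | -0.049 (100%) |
| 10%, 1 SD | -0.089 | -0.086 (97%) | -0.089 (100%) |
| 20%, 0.5 SD | -0.095 | -0.084 (88%) | -0.094 (99%) |
| 20%, 1 SD | -0.203 | -0.185 (91%) | -0.202 (about 100%) |

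The percentage is the imputed bias divided by the bias with removal. Roughly 90-100% of the bias remains, because the shortfall is by construction not predicted by baseline.

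**5. What data a no-session dyad could supply**

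Before Visit 3 the protocol collects the COPM (Visit 1), the Zarit and VABS (by link), and the MoCA and NPI (Visit 2), so a baseline for imputation can exist. At week 4 the Zarit can come back without a session. The other scales generally cannot, because Visit 9 is itself a Zoom visit.

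**The case against.** Several counter-arguments have force.

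- **The rule may have removed nobody.** On the literal reading it does nothing, and even on the intervention-session reading mITT equals ITT if every dyad attended once. A reader might infer that the comparisons were in fact biased. The documents do not support that: the sequence is pieced together from separate sections and no count by arm is given. What stands is lost protection, conditional on the reading.
- **An all-randomised set does not recreate missing outcomes.** A reader might infer that including everyone removes the bias. In simulation that is so only when the week-4 outcomes of the lost dyads are observed. Most of those outcomes need a video visit, and imputation from baseline barely helps. This limits what the fix can achieve.
- **The imputation set is not stated.** It is tempting to say that imputation was confined to the mITT set, or that returned Zarit forms were discarded. The section says neither. It only fails to say that removed dyads are restored, and a Zarit return from a no-session dyad is possible, not shown.
- **The stakes are limited.** The endpoints are secondary and exploratory, Study Design calls the behaviour results explorative and descriptive, and the assumed bias is under one standard error even with entirely one-sided loss. Describing dyads who started is a fair question in a feasibility trial, as a supportive analysis.
- **Participant flow may be reported elsewhere.** The section points to a table that is not included here, so the absence of counts does not show that they were never reported.

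None of this removes the need to say what the rule excludes. The protocol's other provisions do not help: its per-protocol set requires 75% adherence, which is more selective, and dropouts are replaced until there are 30 full-duration cases, which could mask early losses.

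**Conclusion.** The concern holds in conditional form. On the reading that gives the mITT rule any effect, it selects dyads after randomisation and can do so after the caregiver has seen the arm's materials. The secondary and exploratory comparisons are then not fully protected by randomisation, and no stated analysis restores the removed dyads.

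The actual bias cannot be computed. The range of 0.05-0.20 SD rests on assumed one-sided, informative loss of 10-20%; it is zero if nobody was removed and near zero if loss was unrelated to outcome. The supportable gain from a change is recovery of outcomes returned without a session, chiefly the Zarit, plus an open assumption about the rest. The primary endpoint is not affected. The change should be made, but it does not undermine the trial's main feasibility result.

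**What to change.** 1. Make the main set for secondary and exploratory endpoints all randomised dyads in the arm assigned, using every week-4 outcome returned whether or not a session was attended, notably the emailed or posted Zarit. Keep mITT as supportive.
2. Define the video session by visit number.
3. Report, by arm, the dyads randomised, with no session, and analysed, showing replacements separately.
4. Run the multiple imputation over all randomised dyads and say so. State that imputation from baseline alone does not remove bias from unobserved outcomes.
5. Add a sensitivity analysis that imputes worse outcomes for no-session dyads over a stated range, for example 0.5-1 SD, varying the range by arm.

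The cost is a few sentences of SAP wording and a small amount of extra analysis. The downside is slight dilution of the estimate by dyads who never started.

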**Individualized Environmental Design Protocol:** Participants' caregivers will receive standard recommendations of physical environment modifications and caregiving techniques. Physical environmental modifications will include declutter living space, reduce background noise, increase natural light, accommodate for accessibility to commode and areas for drinking and eating. Caregiving techniques will include training for calming demeanor (emotional contagion), needs-driven care to decrease onset of behavioral disruption, and accepting and accommodating approach to behavioral disruption. Individualized sensory stimulation kits will be developed using subjects' preferred sensory stimuli (as determined by the Adult Sensory Profile assessment) and behavioral concerns identified in the COPM. One target behavior and/or time period of the day will be targeted for improvement. Selection of items included in the individualized sensory kit will be determined based on the attached decision tree and sensory mode plans. The sensory kit will be provided via caregiver administration or supervision two scheduled times (once in the morning and once in the afternoon) per day and one time as needed prior to activity or task associated with behavior concern to promote maintained behavioral regulation and adaptive responses.

**Data Analysis:** Due to the nature of feasibility of this study, sample size of 30 participants with cognitive impairment (10 per arm) does not fully power the study. Statistical description of behavior change results will be explorative and descriptive in nature. Per-protocol analysis (PPA) will be performed with 75% or more adherence to program as determined from weekly visits and journals. Power analyses for secondary outcome measures cannot be performed as this study is a preliminary investigation of these secondary outcome measures.

Summary statistics will be tabulated for the behavior change, protocol adherence, and adverse events. The frequencies of behavior change, protocol adherence, and adverse events will be compared between participants within same group and between group for differences.

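### The imputation model is stated only as a regression on baseline, without treatment arm; if run that way, the sensitivity check is weak support for non-significant results

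*Combined protocol and SAP*

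**What the plan says.** The only description of imputation is in the Statistical Analysis section. Secondary and exploratory endpoints are analysed by ANCOVA, with the end-of-intervention mean "adjusted for baseline and then compared among the study arms". A sensitivity analysis is then described in which "multiple imputation was used for missing responses at the end of the intervention period (regressed on baseline". The same sentence adds that "the list of covariates included age of the person with AD at baseline and gender of the caregiver when appropriate". That list most naturally belongs to the ANCOVA, where arm is the factor under comparison and would not be listed as a covariate, so it does not settle what the imputation model contained. Imputation by arm is not mentioned.

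The analysis set is a modified intention-to-treat set: "participants were included in the analysis only if the dyad completed at least one video session". The section concludes: "These sensitivity analyses did not change any of the conclusions drawn from the reported ANCOVA in Table 3 and are not reported here".

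Two other places bear on the point. Research Procedures plans for drop-outs as follows: "researchers will recruit for replacement participants so that the study is completed with 30 entire study duration cases". The Data Analysis paragraph under Study Design gives 10 participants per arm and says: "Statistical description of behavior change results will be explorative and descriptive in nature".

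**The concern.** An imputation model should contain the variable that the analysis model tests. If arm is left out, every missing response is drawn from one regression pooled over the three arms, as though arm had no effect. The completed data then mix real arm differences among the observed with no arm difference among the imputed.

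What is at stake is the robustness statement. The sensitivity estimates are not shown, so the short description of the model is all a reader has for judging the claim that no conclusion changed. If the imputation itself pulls the arms together, agreement with a non-significant ANCOVA is close to automatic and says little.

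**Working it through.** **Inputs from the documents.** Three arms, 10 per arm (Data Analysis); imputation regressed on baseline, and ANCOVA on baseline and arm (Statistical Analysis). No effect size, SD, missing fraction or imputation result is given, so there is no figure of the plan's to reproduce.

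**Assumed inputs.** Outcome SD 1; baseline-outcome correlation 0.6 unless stated; values missing completely at random within arm; effects and losses as shown.

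**Closed form.** Let f_a be the missing fraction in arm a, mu_a its true adjusted mean, and m the pooled mean of the completers. Imputing on baseline alone gives an expected adjusted mean of

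(1 − f_a)·mu_a + f_a·m.

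If f is the same in every arm, m cancels and each contrast becomes (1 − f) times its true value.

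**Equal loss, effect 1.0, 10 completers per arm plus drop-outs:**

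| Drop-outs per arm | Closed form | Simulated, baseline only | Simulated, arm included |
|---|---|---|---|
| 1 | 10/11 = 0.91 | 0.89–0.91 | 0.98–1.01 |
| 2 | 10/12 = 0.83 | 0.81–0.84 | 0.97–1.01 |
| 3 | 10/13 = 0.77 | 0.75–0.77 | 0.98–1.01 |

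The simulations use proper imputations (drawn residual variance and coefficients); ranges cover repeat runs and contrasts. Correlations of 0.3 or 0.8 change little (0.90–0.91 at 1 drop-out, 0.76–0.78 at 3). The bias is about 0.3, 0.55 and 0.85 of the baseline-only estimate's own SD (0.33–0.34, 0.30, 0.28). An effect of 0.5 at 2 drop-outs per arm becomes 0.41, against 0.49 with arm.

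**A second layout: 10 per arm in total, effect 0.8 in both active arms.** At 10%, 20% and 30% missing, baseline-only imputation gives 0.72, 0.63–0.64 and 0.54 (closed form 0.72, 0.64, 0.56). With arm included it gives 0.80–0.82.

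**Unequal loss** (drop-outs in control / middle / third arm, 10 completers each):

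- 1/1/4, means 0/0/1, so m = 1/3. Third arm: (10/14)(1) + (4/14)(1/3) = 0.810. Control: (1/11)(1/3) = 0.030. Contrast 0.78 instead of 1.
- 0/3/3, means 0/0/1. Contrast (10/13) + (3/13)(1/3) = 0.85 (simulated 0.84).
- 0/4/0, means 0/0.5/1, so m = 0.5. Middle arm: (10/14)(0.5) + (4/14)(0.5) = 0.5. No change.
- 0/4/0, means 0/0.2/1, so m = 0.4. Middle arm: (10/14)(0.2) + (4/14)(0.4) = 0.26 (simulated 0.25). Away from zero.
- 0/4/0, means 0/0/1. Middle arm: (4/14)(1/3) = 0.095 (simulated 0.09–0.10), where the true contrast is 0.

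**False positives.** That last shift did not raise them: 1.9% significant, against 4.8% for the observed-case ANCOVA. With no effect in any arm and 2 drop-outs per arm, rejection was 2.0% with baseline only, 5.9% with arm and 5.8% for the observed-case ANCOVA, and the contrasts stayed at zero.

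**What the check can detect** (effect 1.0, equal loss of 1, 2 or 3 per arm, two-sided 5%):

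- Non-significant ANCOVA turning significant, as a share of all trials: 0.0–0.1% without arm, 0.9–1.9% with arm.
- Significant ANCOVA remaining significant: 85%, 69–74% and 57% without arm; 97%, 96% and 93% with arm.

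One reason for the first result, beyond the shrinkage, is that baseline-only imputation reported a mean standard error of 0.38–0.39 while the estimate's actual SD was 0.28–0.34.

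**The case against.** **Arm may have been used.** The description is a short gloss in a condensed paragraph; it does not say that baseline was the only predictor and does not exclude imputation by arm. This stands. A reader might infer that arm was omitted, but the documents show only that it is not named.

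**Nothing may have been missing.** Drop-outs were to be replaced until 30 cases were complete. This does not dispose of the point: the analysis set keeps any dyad with at least one video session, and the section itself speaks of missing responses. The number missing is nevertheless unknown, so every magnitude above is conditional.

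**A null-leaning check can be a strict one.** For a significant ANCOVA under equal loss, surviving baseline-only imputation is harder than surviving the corrected version. This stands, and it limits the criticism to non-significant results. Table 3 is not in the documents, so it cannot be told which kind of conclusion was being confirmed.

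**The correction changes little.** With arm included, the imputed result sits close to the observed-case ANCOVA, and few verdicts would change. This also stands; the gain is a valid, visible check and not new information.

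**Conclusion.** The point holds conditionally and is minor. The imputation model as stated does not match the analysis it feeds. If it was run as stated, and if some outcomes are missing and the arms truly differ, the arm contrasts are generally biased. Under the assumptions above, equal loss of 1 to 3 dyads per arm takes a 1.0 SD effect to about 0.9, 0.8 and 0.75 SD. With no missing values, or no true differences among the arms, there is no bias.

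Three stronger readings are tempting, and the documents do not support them:

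- A reader might infer that the bias is always toward no difference. With unequal loss across three arms, a contrast can also stay the same or move away from zero.
- A reader might infer that the no-change statement is worthless. It is weak support for non-significant results only; for significant results under equal loss it is conservative.
- A reader might infer that the trial's findings are affected. The primary chi-square test and the main ANCOVA do not use the imputed data, and the protocol already treats the behaviour results as exploratory and descriptive.

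**What to change.** First, state the imputation model and the number of missing responses per arm for each endpoint. If arm was already included, one sentence closes the point.

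If it was not, add arm as a predictor together with the ANCOVA covariates: baseline, plus age and caregiver gender where the ANCOVA uses them. Use one model with an arm term; separate models within each arm would be unstable at about 10 per arm. Rerun, and report the estimates with intervals beside the main ANCOVA. Say that they should lie close to the observed-case result because both rest on the same missing-at-random assumption, so agreement gives only limited reassurance.

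The cost is one added predictor in the SAS imputation step, a rerun and a few table rows. Intervals are slightly wider than for the observed-case ANCOVA: in the simulations, a mean standard error of 0.36–0.37 against 0.36.
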